8.4 Data Presentation Conventions

Continuous safety variables (e.g., clinical laboratory values and vital signs) will be listed to the same precision as the source data. Derived variables will be calculated and listed using the same precision as the value(s) from which they were derived.

For the tabular reporting of descriptive statistics:

- Continuous variables: the same number of decimal places as in the raw data will be presented when reporting minimum and maximum, 1 more decimal place than in the raw data will be presented when reporting mean and median, and 2 more decimal places than in the raw data will be presented when reporting SD.
- Categorical/discrete variables: the frequency count and the percentage (of available data) for each class of the variable will be presented and will be displayed in the form XX (XX.X%) where the percentage is in parentheses. All percentages will be presented to 1 decimal place, unless otherwise specified. Percentages equal to 100 will be reported as 100% and percentages will not be presented for zero frequencies. Unless otherwise specified, percentages will be calculated based on the number of patients specified by the appropriate population definition.
- Date variables: formatted as DDMMYY for presentation. Time will be formatted in military time as HH:MM for presentation.

Extra measurements (such as unscheduled or repeat assessments) will not be included in summary tables but will be included in patient listings. They will be used in summary tables which are not 'time specific', for example, summaries of minimum maximum, first, last, average post dose values.

All tables, listings, figures will be produced in landscape orientation using Arial 9-point font. Output files will be created in rich text file (RTF) format.

Missing or invalid data will be generally treated as missing, not imputed, unless otherwise stated (see Section 9.5).

The table, figures and listing shells and table of contents as part of this SAP provide the expected layout and titles of the tables, listings, and figures. Any changes to format, layout, titles, numbering, etc. will not necessitate a revision to the SAP, nor will it be considered a deviation from planned analyses. Only true differences in the analysis methods or data handling (e.g., change in the population used, change from statistical method/assumption listed, transformation of data type [e.g., continuous data transformed to categorical], exclusion of planned analysis, etc.) or additional unplanned analyses will necessitate a revision to this SAP. The appropriate listings supporting the tables will be included and are not specified in the individual sections throughout the document.

8.5 Treatment Comparisons

The following labels for dose level will be used on all tabulations, in the following order:

| Phase 2A Expansion | | | | |
|--|---|---|---|-----------------|
| Group 1 Extremity STS 5-Day Infusion (N=00) | Group 2 Unresectable STS 3-Day Infusion (N=00) | Group 2 Unresectable STS 5-Day Infusion (N=00) | Group 3A Head and Neck 5-Day Infusion (N=00) | Total (N=00) |

8.6 Definitions, Computations, Derived Data

- Screening: Screening is defined as ≤ 28 days prior to Cycle 1 Day 1 prior to the first study drug administration.
- Baseline: Measurements taken at Screening or prior to receiving the first dose of study drug; whichever is latest.
- Study Day and Cycle Day follows the CDISC standard and is defined as:
 - On-study Assessment Days (Assessment date – First date of study drug dosing of the first cycle) + 1, where the assessment date is on or after the first date of dosing of the first cycle.
 - Screening Days (Assessment date – First date of study drug dosing of the first cycle), where the assessment date is before the first date of dosing of the first cycle. For this protocol, screening days are from Day -28 to -1.
 - There will be no Study Day 0.
 - “Study Day x” (where $x > 0$) refers to the number of days from first dosing date in Cycle 1. For example, Study Day 1 is Cycle 1 Day 1.
- Visit Nomenclature: Nominal visits nomenclature on the CRFs and the scheduled visit will be used for summary tables.

- Scheduled visits for the Treatment Period are: "Screening", "Cycle x Day 1" (where x = 1, 2, 3, ... 9), Days 1, 2, 3, 4, 5, 10, 17, etc.
- Safety follow-up visit is 28-34 days after the last dose of study drug and on-site.
- Long Term follow-up visits are every 12 weeks (on or off site).
- Assessment for response and tumor burden is planned every 6 weeks and at Safety follow-up and long-term follow-up.
- The objective response rate (ORR): Percentage of patients whose best objective response recorded from the start of the treatment until disease progression/recurrence is a CR or PR according to RECIST 1.1 criteria.
- Best Overall Response (BOR) is defined as the best response recorded in the case report form after the start of the study treatment.
- A determination of the recommended Phase 2 dose (RP2D) will be based on the safety and tolerability from every cycle of treatment, not just Cycle 1. The RP2D will be determined based on all available data, including PK/PD analysis, tolerability that will include the incidence and severity of DLTs, other AEs and the evidence for biological activity at each dose level tested. The RP2D can be defined by an SQP33 protodrug dose and a SQL70 biopolymer volume.
- 1 year = 365.25 days. Year is calculated as (days / 365.25) and will be rounded to 1 digit after the decimal point (tenths) for presentation purposes.
- 1 month = 30.4375 days. Month is calculated as (days / 30.4375) and will be rounded to 1 digit after the decimal point (tenths) for presentation purposes.
- 1 pound = 0.454 kg and 1 kg = 2.2 pounds
- 1 inch = 2.54 cm and 1 cm = 0.3937 inches
- Body mass index (BMI) calculated as [weight (lbs) / height (in)²] x 703.
- Age will be calculated in years relative to the date of study consent based on the following SAS statement: Age = ([Consent Date - Date of Birth] / 365.25) and will be rounded to 1 digit after the decimal point (tenths) for presentation purposes.
- Doxorubicin equivalent: 1 g of SQP33 protodrug is equivalent to 0.7153 g of doxorubicin hydrochloride.

9. GENERAL CONSIDERATIONS FOR DATA ANALYSES

The listings, figures and summary tables for the disposition, baseline characteristics, study drug administration, safety, and efficacy data will be the responsibility of the study Biostatistician at Vantage Data Designs.

The currently supported version of SAS software (9.4 or later) will be used to perform all data analyses. The actual SAS version used will be presented in the Clinical Study Report.

All data in the database will be presented in the data listings. Unless otherwise stated, all listings will be sorted by Phase 2A expansion group, patient number, and assessment date/time.

Unless otherwise stated, continuous variables will be summarized using descriptive statistics including number of non-missing observations, mean, standard deviation, median, minimum and maximum values. Categorical variables will be summarized with frequency counts and percentages. The population size (N for sample size and n for available data) and the percentage (of available data) for each class of the variable will be presented.

In general, only data from nominal protocol scheduled visits will be included in the summary tables. They will be used in summary tables which are not 'time specific', for example, summaries of first, last, minimum, maximum, and average post dose values. Data from unscheduled visits will not be included in the summary tables but will be included in the listings.

The Efficacy Evaluable analysis set will be the primary basis for the response efficacy endpoints and the Full Analysis Set for time-to-event endpoints (time-to-event has 'censoring' rules in place for missing data). The Safety analysis set will be used for the safety summaries.

9.1 Multicenter Studies

Data from all participating sites will be pooled for the analysis.

9.2 Other Strata and Covariates

Not applicable for this study.

9.3 Examination of Subgroups

For the Phase 2A dose expansion portion of this study, there are no pre-defined exploratory subgroup analyses planned. However, if the data warrant (high ORR, etc.), subgroup analyses may be performed and will be discussed fully in the clinical study report.

9.4 Multiple Comparisons and Multiplicity

Not applicable for this study.

9.5 Missing Data and Dropouts

The issue of how to handle missing data caused by dropouts in clinical studies is a research topic that is still under development in statistical literature. As has been noted in the ICH-E9 guideline, “no universally applicable method of handling missing values can be recommended”. The best approach is to minimize the chance of dropouts at the design stage of the clinical study and during study monitoring. Every effort will be made to collect data for all timepoints.

In general, data will be analyzed as received from the clinical database. Hence, missing values will not be replaced by imputed values except for the following situations:

9.5.1 Adverse Events

Adverse events with missing or partial dates will be handled such that in the absence of contradictory information an AE is classified as “treatment emergent”. So, for a missing start date (where the stop date is after the date of first study drug administration) the start date will be imputed as the first study drug administration date. Similarly, for a missing stop date, the stop date will be imputed as the date of last visit.

- If a partial date is recorded, the following convention will be used to assign the AE: If a start date is missing the day information and the month/year is the same as the first study drug administration date, then use the first study drug administration date, else ‘01’ will be used for the day. If a start date is missing the month and the year is the same as the first study drug administration date, then use the first study drug administration date, else ‘January’ will be used for the start month.
- If a stop date is missing the day information and month/year is the same as the last study date, then use the last study date, else the last day of the given month will be used for the stop day. If a stop date is missing the month and the year is the same as the last study date, then use the last study date, else ‘December’ will be used for the stop month.

9.5.2 Concomitant Medications

If the stop date of a concomitant medication is missing, then the medication will be treated as ongoing. If the start date of a medication is missing, the stop date will be used to determine whether or not it is concomitant. Medications with other incomplete start dates will be identified as concomitant using the same algorithm as above for TEAE, if the stop date information is insufficient for the determination.

If the start date is missing, the medication will be considered to have started prior to the study. It may also be considered concomitant, depending on the stop date or lack thereof.

9.5.3 Other Situations

For patients who are withdrawn from the study prior to study completion, all data compiled up to the point of discontinuation will be used for analysis. All withdrawals will be included in all analyses up to the time of withdrawal.

Extra measurements (such as unscheduled or repeat assessments) will not be included in summary tables but will be included in patient listings. They will be used in summary tables which are not 'time specific', for example, summaries of first, last, minimum, maximum, and average post dose values.

The original data will always be presented in the listings.

10. STUDY POPULATION

All disposition, baseline and demographic analyses will be conducted on both the safety and efficacy evaluable populations. Unless specified elsewhere, baseline is defined as the last recorded value prior to the administration of the first dose of study treatment (SQL70 Biopolymer).

10.1 Patient Enrollment

Patient enrollment will be presented for all enrolled patients and will be summarized by investigative site, expansion group and overall total based on:

- Number of patients who were enrolled.
- Number of patients who qualified for the Safety Population
- Number of patients who qualified for the Efficacy Evaluable Population
- Number of patients who were enrolled but not treated with study drug (i.e., screen failures)

A listing of patient enrollment will be provided for all enrolled patients. A listing of whether or not all inclusion and exclusion criteria were met and if not, which criteria were not met by patient, will also be presented.

10.2 Patient Disposition

The patient disposition summary will be summarized by expansion group and will include:

- Reasons for treatment discontinuation

- Number of patients ongoing in the study
- Reasons for study discontinuation
- Summary of time on study described as the time in days from the first dose until the last recorded visit.

10.3 Protocol Violations or Deviations

A protocol deviation is any noncompliance with the clinical trial protocol or Good Clinical Practice (GCP). The noncompliance may be either on the part of the patient, the investigator, or the study site staff. Capturing every specific protocol deviation was not part of the eCRF database. Protocol deviations will be identified and documented by Shasqi study monitors/project manager outside the eCRF database prior in an ongoing manner and finalized prior to database lock. All protocol deviations will be reviewed by Shasqi medical monitors in an ongoing fashion. Protocol deviations will be detailed in patient listings and discussed in the clinical study report.

10.4 Demographics

Demographic characteristics will include

- Age (years) (descriptive statistics)
- Age category (years)
 - ≥ 18 - < 66
 - ≥ 66 - < 75
 - ≥ 75
- Sex (male, female)
- Race
- Ethnicity

The categorical (discrete) variables will be summarized using counts and percentages. The continuous variables will be summarized using mean, median, standard deviation, and range (maximum, minimum).

10.5 Baseline Characteristics

Baseline characteristics will include (but not limited to):

- ECOG performance status (0,1)
- Type of cancer e.g., liposarcoma
- Stage of disease at study entry
 - Localized

- Locally Advanced
- Metastatic
- Primary location of disease
- Metastatic site locations
- Number of metastatic sites
- Response to most recent prior therapy
- Prior therapy received for cancer being studied
 - Systemic anti-cancer therapies (per Shasqi medical review)
 - Prior radiation
 - Prior surgery
 - Prior radiotherapy
-
- Prior treatment with immuno-oncology therapies that could alter the body's immune response against cancer. This data will be identified by medical monitor review of prior lines of therapy.

10.6 Medical History

Medical History will be coded using the Medical Dictionary for Regulatory Activities (MedDRA) version 24.1. Data will be descriptively summarized by the System Organ Class (SOC) and preferred terms (PT). The summary table will be sorted by overall frequency of recorded medical history and will show the number and percentage of patient's medical history by SOC and preferred term by expansion group.

10.7 Concomitant Medications

Concomitant medications will be coded by WHO Drug coding dictionary (September 2020). Data will be descriptively summarized by Anatomical Therapeutic Chemical (ATC) system Level 1, and drug preferred name. The summary tables will be sorted by overall frequency of recorded use and will show the number and percentage of patients taking each medication by ATC Level 1 and preferred term by expansion group. Patients who take the same medication (in terms of the ATC Level 1 and preferred name) more than once will only be counted once for that medication. Medications with end dates prior to dosing will not be included in these summaries.

10.8 Study Drug Administration: Exposure and Modifications

The SQ3370 Investigational Product consists of 2 components:

- (1) Intratumoral injection of a prodrug activating biopolymer (SQL70: 10 mL or 20 mL).

(2) Five (or three) consecutive days of intravenous (IV) infusions of a trans-cyclooctene (TCO)-modified protodrug of Dox with attenuated cytotoxic activity (SQP33) for a 21-day cycle.

An individual cycle of treatment is defined as a 3-week (21-day) period wherein the SQL70 biopolymer is injected into a lesion or lesions on Day 1 followed by 3-5 consecutive daily infusions of SQP33 protodrug (Day 1-5 or in Phase 2a Group 2 subset will receive Day 1-3). In Phase 1 patients assigned to receive 20 mL SQL70, no more than 2 lesions may be injected (10 mL each) during the treatment cycle with the exception of a “regional cluster of lesions” defined as tumors that are contiguous, in apposition to each other, or are within 5 cm of each other.

For Phase 2a the treatment regimens are:

- Group 1 Extremity STS: 20mL SQL70 Biopolymer + 250 mg/m² (12x Dox Eq)
SQP33 Protodrug on a 5 day infusion schedule
- Group 2 Unresectable STS :10mL SQL70 Biopolymer + 250 mg.m² (12x Dox Eq)
SQP33 Protodrug on a 5 day infusion schedule
- Group 2 Unresectable STS :10mL SQL70 Biopolymer + 250 mg.m² (12x Dox Eq)
SQP33 Protodrug on a 3 day infusion schedule
- Groups 3A Head and Neck:10mL SQL70 Biopolymer + 250 mg.m² (12x Dox Eq)
SQP33 Protodrug on a 5 day infusion schedule.

Study treatment (SQP33 and SQL70) received will be summarized as described below:

Study Drug Administration (Exposure):

- Number of cycles
- Duration of Therapy
- Average Duration of SQP33 Infusions
- Total SQP33 Cumulative Dose (mg/m²)
- Total SQL70 Cumulative Dose (mg/m²)
- Total Doxorubicin Equivalent Cumulative Dose (mg/m²)
- Highest SQP33 dose administered
- Highest Doxorubicin Equivalent dose administered

Dose Modifications:

1. SQL70 Biopolymer

- a. Injection interruption

- b. Dose increase of biopolymer (10 mL to 20 mL)
- 2. SQP33
 - a. Dose interruption of infusion (bag change is not an interruption)
 - b. Dose reduction (Y or N, and by summary units)
 - c. Dose increase (Y or N, and by summary units)

Details concerning the derivation of these measures are below.

- Highest SQP33 Dose Administered = Defined as the largest (or maximum) SQP33 dose administered (mg/m²)
- Total SQP33 Cumulative Dose received (mg/m²) = Defined as the sum of all SQP33 doses (mg/m²) received
- Average Duration of infusion = As recorded on CRF, summarized using the average infusion duration in minutes
- Duration of therapy (median (min/max), mean) = As recorded on CRF, summarized using the time in days from first dose to last dose

These study drug administration and exposure parameters will be summarized using descriptive statistics. Continuous variables by the mean, standard deviation, median, minimum, and maximum values. Categorical variables by the number and percentage of patients in each category.

Additional information regarding study drug administration will be presented in the patient listings.

11. EFFICACY ANALYSIS

Time to event variables will be estimated using K-M methodology. Binary variables will be summarized by binomial response rates and their corresponding two- sided 95% exact CI. Categorical variables will be summarized using tables presenting counts and percentages for each category. Quantitative variables will be summarized using the mean, median, minimum, and maximum values, and standard deviation.

For the Dose Expansion portion of this study, the Treated/Full analysis set will be utilized for efficacy analyses. This analysis set consists of all patients who receive at least 1 dose of SQL70 biopolymer and 1 dose of SQP33 protodrug. The Efficacy Evaluable analysis set will also be utilized for comparison purposes. This analysis set consists of all patients who receive at least 1 dose of SQL70 biopolymer and 1 dose of SQP33 protodrug and undergo at least 1 post baseline tumor evaluation. The efficacy endpoints will be assessed by the

investigator assessed RECIST v1.1, and will be summarized in tables, listings and/or figures as outlined in the sections below.

Additional analyses may be performed to assist the Sponsor in planning future studies.

In addition to the summary tables, efficacy data will also be presented in the individual patient listings.

11.1 Objective Response Rate (Groups 1, 2, and 3a)

Objective response rate (ORR) is defined as the number and percentage of participants with a best overall response (BOR) of confirmed CR or PR. BOR is defined as the best response designation, recorded between the date of enrollment and the date of the initial objectively documented tumor progression per RECIST v1.1, date of death from any cause, or the date of subsequent therapy, whichever occurs first. For participants without documented progression or subsequent therapy, all available response designations will contribute to the BOR determination.

The overall response rate (ORR) will be summarized with the number and percentage of patients along with the corresponding two- sided 95% exact confidence interval (CI). by Phase 2a expansion group. In addition, a swimmer's plot will be constructed. This will depict time on study, CR/PR date, disease progression (and/or death) date, end of treatment/study date, etc. This swimmers plot will also help visualize the other efficacy endpoints using RECIST1.1 described below (i.e., duration of response, disease control rate, and disease control rate).

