6.18. CT/MRI TUMOR IMAGING & MEASUREMENTS

All measurements should be taken and recorded in metric notation using a ruler, calipers, or a digital measurement tool.

The same method of assessment and the same imaging technique regarding modality, ideally the same scanner, and the use of contrast should be used in a participant throughout the study

to optimize the reproducibility of the assessment of existing and new tumor burden and improve the accuracy of the assessment of response or progression based on imaging.

Assessment should be performed:

- During screening
- Every 6 weeks (-7-day window) from Cycle 1 Day 1 until end of treatment
- At the Safety Follow-Up Visit, if not performed in the previous 6 weeks
- If a patient comes off treatment due to non-RECIST progression, a scan should be obtained during Long Term Follow Up, until radiographic progression is noted.
- Additional scans may be conducted at other time points if deemed clinically appropriate

Scans will be read at the study site. Scans must include chest, abdomen, and pelvis, as well as any other areas of disease, whether or not measurable, present at screening and/or follow-up, including extremities.

Computed Tomography (CT) / Magnetic Resonance Imaging (MRI): Scans are required to document disease status (including chest, abdomen, pelvis, and other regions as clinically indicated). A brain scan is required to exclude brain metastasis if clinically indicated.

Clinical Examination: Imaging-based evaluation is preferred to evaluation by clinical examination unless the lesion(s) being followed cannot be imaged but are assessable by clinical examination. Tumors may also be assessed utilizing visual or palpable lesions on physical examination, including full assessment of all known metastases.

Copies of redacted radiology reports and interventional radiology procedure notes may be obtained for quality control.

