6.18.1. Target and Non-Target Tumor Baseline Recording

To assess objective response or future progression, it is necessary to estimate the overall tumor burden at screening and use it as a comparator for subsequent measurements.

Target Lesions

When more than 1 measurable lesion is present at baseline, all lesions up to a maximum of 5 lesions total (and a maximum of 2 lesions per organ) representative of all involved organs should be identified as target lesions and will be recorded and measured at baseline (this means that, in instances where patients have only 1 or 2 organ sites involved, a maximum of 2 and 4 lesions, respectively, will be recorded).

A sum of the diameters (longest for non-nodal lesions, short axis for nodal lesions) for all target lesions will be calculated and reported as the baseline sum diameters. The baseline sum of the

diameters will be used as reference to further characterize any objective tumor regression in the measurable dimension of the disease.

If a lesion “fragments” as it shrinks, the individual lesion diameters should be added together to calculate the target lesion size. If lesions coalesce and become inseparable, the longest diameter of the merged lesions should be used as the lesion size.

Note: Only target lesions can be selected for SQL70 biopolymer injection.

Non-Target Lesions

All other lesions (or sites of disease) should be identified as non-target lesions and should also be recorded at baseline. Measurements are not required, and these lesions should be followed as “present,” “absent,” or in rare cases “unequivocal progression.”

See RECIST v1.1 ([Eisenhauer 2009](#)) for additional details.

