8.4.2.2. Secondary Endpoints

The endpoints below will be assessed by the Investigators. Time to event variables will be estimated using K-M methodology. Medians using the log-log transformation will be computed. Binary variables will be summarized by binomial response rates and their corresponding two-sided 95% exact CI. Quantitative variables will be summarized using the mean, median, minimum, and maximum values, and standard deviation. Categorical variables will be summarized using tables presenting counts and percentages for each category. Further explanation, description, and landmark analyses (e.g., at 12, 24 months) will be provided in the statistical analysis plan finalized before the first database lock.

- ORR is defined as the number and percentage of participants with a BOR of confirmed CR or PR. BOR is defined as the best response designation, recorded between the date of enrollment and the date of the initial objectively documented tumor progression per RECIST v1.1, date of death from any cause, or the date of subsequent therapy, whichever occurs first. For participants without documented progression or subsequent therapy, all available response designations will contribute to the BOR determination.
- DCR is defined as the proportion of participants whose BOR is CR or PR or SD among all randomized participants.

- DoR is defined as the time recorded between the date of enrollment and the date of the initial objectively documented tumor progression per RECIST v1.1, date of death from any cause, or the date of subsequent therapy, whichever occurs first. DoR will be evaluated for responders (i.e., participants with confirmed CR or PR) only.
- Histopathologic Response
- Surgical outcome amputation/limb salvage vs. planned
- Time to local-regional progression or distant progression is defined as the time between the date of enrollment and the date of local recurrence/relapse or distant progression.
- Local-recurrence-free survival is defined as time between the date of enrollment and the date of local recurrence/relapse or death from any cause, whichever occurs first.
- Distant-recurrence free survival is defined as time between the date of enrollment and the date of distant recurrence/relapse or death from any cause, whichever occurs first.
- Disease-free survival is defined as the time between the date of enrollment and the date of recurrence/relapse or death from any cause, whichever occurs first.

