11.6 Time to First Subsequent Therapy (Groups 1, 2 and 3a)

Time to first subsequent therapy (TFST) is defined as the time between the date of first dose of study drug to the date of first new anti-cancer therapy (subsequent therapy). .

At this time, there is not enough information regarding this endpoint. The data collection and planned analysis of this endpoint will be discussed in the next version of this SAP after the safety run-in and/or Simon Stage 1 analysis. However, Kaplan-Meier methods will be utilized for data analysis of this endpoint.

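### Group 1's planned resection is not named as closing the best-response window, and SAP 8.6 conflicts with SAP 11.1, so the counts behind 4/15 and 14/46 are not uniquely defined

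*SAP*

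**What the plan says.** **Main definition.** SAP 11.1 defines ORR as the number and percentage of participants whose BOR is a confirmed CR or PR. BOR is the best designation up to progression, death or subsequent therapy, and "For participants without documented progression or subsequent therapy, all available response designations will contribute to the BOR determination". Protocol 8.4.2.2 uses the same window, "recorded between the date of enrollment and the date of the initial objectively documented tumor progression per RECIST v1.1", with the same other closing events. Neither names surgery.

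**Second definition.** SAP 8.6 says: "Best Overall Response (BOR) is defined as the best response recorded in the case report form after the start of the study treatment". Its ORR bullet counts patients whose best response "recorded from the start of the treatment until disease progression/recurrence is a CR or PR according to RECIST 1.1 criteria". It does not ask for confirmation.

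**Surgery and scans in Group 1.** Patients without progression are evaluated after two cycles and again after four, then go to surgery (SAP 2.3; Protocol 3.1.4.1). Patients with a response or clinical benefit may defer surgery for up to four more cycles. Patients with a response may receive up to four cycles after surgery. Imaging is scheduled "Every 6 weeks (-7-day window) from Cycle 1 Day 1 until end of treatment". It continues in long-term follow-up until RECIST progression (Protocol 3.1.7 and 6.18; Appendix H note N).

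**The resected tumor.** Protocol 6.18.1 states: "Only target lesions can be selected for SQL70 biopolymer injection". Table 6 of Protocol 6.18.2 defines target-lesion CR as disappearance of all target lesions and makes no exception for surgical removal.

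**Decision rules.** Group 1 goes on at 4 or more responses in 15, and efficacy is considered at 14 or more in 46 (SAP Section 4; Protocol 8.3).

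**The concern.** ORR is the count on which both Simon boundaries operate, in the largest Phase 2a group. If a patient is resected without prior progression, the text gives no instruction to stop collecting response designations at that date. A later scan shows the injected target lesion gone because a surgeon removed it. If an investigator recorded that as CR or PR, a programmer following SAP 11.1 literally could include it, and one following SAP 8.6 would include it without confirmation. Another programmer could treat the resection as subsequent therapy and exclude it. The same data would give different counts, and the larger count would mix surgical removal with drug effect.

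The wording also leaves open what happens to a response first seen on the last scan before surgery. SAP 11.1 requires confirmation and SAP 8.6 does not.

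SAP 11.6 is the only place that glosses subsequent therapy. It says that data collection and analysis of its endpoint "will be discussed in the next version of this SAP after the safety run-in and/or Simon Stage 1 analysis". That clarification could come after the 4/15 decision.

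**Working it through.** **Step 1. Is resection a closing event?** The passages point both ways.

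- Toward yes: SAP 11.6 equates subsequent therapy with the first new anti-cancer therapy. Inclusion criterion 10 (Protocol 4.1.1) lists surgery among anticancer treatments. SAP 10.5 lists prior surgery under prior therapy for the cancer.
- Toward no: the end-of-treatment reasons in Protocol 3.1.5 name radiotherapy or tumor-directed treatment outside the protocol. Group 1 surgery is inside the protocol, and study dosing may resume after it.

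The documents do not settle it.

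**Step 2. Reproduce the design.** Inputs from SAP Section 4: p0 = 0.20, p1 = 0.35, stop at 3 or fewer of 15, reject at 13 or fewer of 46. Let X1 ~ Bin(15, p) and X2 ~ Bin(31, p).

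- Early termination: P(X1 ≤ 3) at 0.20 = 0.648
- Expected sample size: 15 + (1 − 0.6482) × 31 = 25.91
- P(meet 14/46) = Σ over x = 4…15 of P(X1 = x) × P(X2 ≥ 14 − x) = 0.0498 at 0.20 and 0.7046 at 0.35

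All four agree with the stated 0.648, 25.91, 0.0498 and 70.5%.

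**Step 3. Extra counted patients at the final analysis, true ORR 20%.** Stage 1 is passed on true responses and exactly k extra patients are counted at the end, so 14 becomes 14 − k in the sum.

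| k | P(meet 14/46) |
|---|---|
| 0 | 0.0498 |
| 1 | 0.0863 |
| 2 | 0.1355 |

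**Step 4. One extra counted patient at Stage 1, true ORR 20%.** Without it, P(X1 ≥ 4) = 1 − 0.6482 = 0.3518. With it, three true responses suffice. P(X1 = 3) = 455 × 0.2³ × 0.8¹² = 0.2501, so the chance of continuing is 0.3518 + 0.2501 = 0.602.

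**Step 5. The opposite direction, true ORR 35%.** If exactly k true responders are not counted at the final analysis, 14 becomes 14 + k. The probability is 0.6264 for k = 1 and 0.5295 for k = 2, against 0.7046. This is a loss of power only if 35% was meant as a rate before confirmation.

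The values of k are assumptions. The documents give no frequency for either event.

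**The case against.** Several points on the other side have force.

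- **Resection may already close the window.** On the reading supported by SAP 11.6, SAP 10.5 and inclusion criterion 10, it does. That reading is reasonable, but Protocol 3.1.5 and the post-operative cycles pull against it, and no sentence chooses.
- **RECIST v1.1 is incorporated by reference** and may have a rule for resected lesions. It could not be consulted here. The SAP's own summary in Section 20 has none.
- **The route is narrow.** An investigator would have to score surgical removal as a response and, under 11.1, have it confirmed. Post-operative cycles are for patients who already had a response. A patient resected after progression has a closed window already.
- **ORR is secondary**, and Section 4 says other evidence of benefit will be reviewed before a final determination. The same section also says that the trial will be stopped, or the drug rejected, at the lower counts. The SAP is still a draft (Version 0.1) and defers several Group 1 endpoints to a later version, but ORR is not one of them.

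A reader might also infer three stronger things that the documents do not support. First, that the plan tells sites to score removal as CR; it only fails to exclude it. Second, that a response first seen after Cycle 4 can be confirmed only by a post-operative scan. Protocol 6.18 allows additional scans when clinically appropriate, and responders may defer surgery, so confirmation before surgery is possible but not assured. Third, that requiring confirmation before surgery must cut power below 70.5%. ORR is already defined as confirmed, so nothing is lost if 35% is the confirmed rate.

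**Conclusion.** The point holds as a defect in the endpoint definition. As written, SAP 11.1 and Protocol 8.4.2.2 allow post-operative designations to count in Group 1, and SAP 8.6 contradicts 11.1 on confirmation and on when BOR ends. The counts for 4/15 and 14/46 are therefore not unique.

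The figures are conditional illustrations, not estimates of the trial's error rate. They apply only if a misclassification occurs, at the assumed true ORR. Given one such patient at the final analysis, 5.0% becomes 8.6%; given one at Stage 1, the chance of continuing goes from 35.2% to 60.2%. The nominal design figures are correct and the boundaries need no change. The ambiguity is certain and its frequency is unknown, so this should be fixed before the Stage 1 review.

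**What to change.** Before Stage 1 data are reviewed:

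1. Add to SAP 11.1 and Protocol 8.4.2.2: *For Group 1, BOR and ORR use only assessments made before the first on-study resection of a target lesion. Later status is reported under histopathologic response, surgical outcome and disease-free survival.*
2. Replace the ORR and BOR bullets in SAP 8.6 by a reference to 11.1, so that confirmed CR or PR is the only definition.
3. Keep confirmation as already stated. A CR or PR first seen on the last pre-surgical scan, with no later scan before surgery, is not counted in either Simon rule. Report ORR including such responses as a sensitivity analysis.
4. If only the SAP is changed, log it in Section 16, which now lists no departures from the protocol.

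The cost is a few sentences and one extra table, with no new visits or scans. Capture of the surgery date on the eCRF should be checked.

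There are two downsides. Some true responders may reach surgery unconfirmed and go uncounted; if the 35% target was meant as a rate before confirmation, qualify the stated 70.5% power. The cut-off also sets aside post-operative response readings in metastatic patients whose other lesions are injected after surgery; these can be described separately.
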